All data will undergo a cleaning process, evaluating four key aspects: consistency, completeness, validity, and uniformity. Consistency is checked to ensure that the data are coherent and that harmonized codes and labels are used. Completeness ensures that the data are fully filled out and ready for use. Validity verifies that the data meet the required standards and fall within the established range. Uniformity ensures that the data are not duplicated and cannot be confused with other entries.

Subsequently, all relevant information will be extracted, creating a copy of the original record, which will be sent to the requester in tabular format (Microsoft Excel). The principal investigator or their delegate will import the Excel file into RStudio and Jamovi. Unstructured data will be obtained through a manual search of the patients' medical records, ensuring that the information is accurate, authentic, attributable, complete, consistent, legible, timely, and durable. These will be manually recorded in a flat file (Microsoft Access) and subsequently transferred to RStudio and Jamovi for analysis.

The following ICD-10 codes are considered key data for searching patient medical records:

- B200: HIV disease resulting in mycobacterial infection.
- B201: HIV disease resulting in other bacterial infections.
- B202: HIV disease resulting in cytomegalovirus disease.
- B203: HIV disease resulting in other viral infections.
- B204: HIV disease resulting in candidiasis.
- B205: HIV disease resulting in other mycoses.

- B206: HIV disease resulting in *Pneumocystis carinii* pneumonia.
- B207: HIV disease resulting in multiple infections.
- B208: HIV disease resulting in other infectious or parasitic diseases.
- B209: HIV disease resulting in unspecified infectious or parasitic disease.
- B210: HIV disease resulting in Kaposi's sarcoma.
- B211: HIV disease resulting in Burkitt's lymphoma.
- B212: HIV disease resulting in other types of non-Hodgkin's lymphoma.
- B213: HIV disease resulting in other malignant tumors of lymphoid, hematopoietic, and related tissues.
- B217: HIV disease resulting in multiple malignant tumors.
- B218: HIV disease resulting in other malignant tumors.
- B219: HIV disease resulting in unspecified malignant tumors.
- B220: HIV disease resulting in encephalopathy.
- B221: HIV disease resulting in lymphoid interstitial pneumonitis.
- B222: HIV disease resulting in cachectic syndrome.
- B227: HIV disease resulting in multiple illnesses classified elsewhere.
- B230: Acute HIV infection syndrome.
- B231: HIV disease resulting in generalized lymphadenopathy (persistent).
- B232: HIV disease resulting in immunologic and hematologic abnormalities, not elsewhere classified.
- B238: HIV disease resulting in other specified conditions.
- B24X: Human immunodeficiency virus (HIV) disease, not otherwise specified.
- F024: Dementia in human immunodeficiency virus (HIV) disease (B22.0†).
- Z21X: Asymptomatic human immunodeficiency virus (HIV) infection status.

All information on the variables of interest will be extracted from the clinical records. The process of data collection and form completion will be carried out by personnel from the Clinical Research Unit, following training to ensure standardized data capture. Quality

control of the data will be performed, including the review of codes, missing data, and any incorrect or improperly transcribed characters, according to the variable, by the researchers before the dataset is purified for analysis.

Study Population

All patients who meet the defined selection criteria within the established time frame for the search will be included:

- Inclusion Criteria:
 - Male or female patients aged 18 years or older.
 - Individuals with a confirmed HIV diagnosis.
 - Individuals enrolled in EPS SURA during the study period.
 - Patients receiving treatment with the TAF/FTC/BIC regimen.
- Exclusion Criteria:
 - Patients with a concurrent diagnosis of tuberculosis.
 - Pregnant patients during the study period.
 - Patients with virologic failure.
 - Patients who started treatment with TAF/FTC/BIC but changed providers or discontinued treatment before completing six months of therapy.

Variables

Variable Name	Definition	Nature	Measuring Level
Primary diagnosis of HIV	Patient with primary ICD-10 diagnosis of: B200, B201, B202, B203, B204, B205, B206, B207, B208, B209, B210, B211, B212, B213, B217, B218, B219, B220, B221, B222, B227, B230, B231, B232, B238, B24X, F024 or Z21X	Qualitative	Text
Diagnosis date	Date of first confirmed repeat HIV diagnosis recorded in the medical record	Quantitative, continuous	dd/mm/yyyy
Date of birth	Patient's date of birth	Quantitative, continuous	dd/mm/yyyy
Sex	Sex defined by patient's medical history	Qualitative	0: Female; 1: Male.
Race	Race defined by patient's medical history	Qualitative	Texto

Type of insurance	Insurance from the health system to whom the patient is covered.		0: Public 1: Private	
Residence department	Department of Colombia where the patient lives	Qualitative	Text	
AHT	Patient with hypertension marked in electronic medical record	Qualitative	0: No 1: Yes	
Diabetes Mellitus	Patient with diabetes marked in electronic medical record	Qualitative	0: No 1: Yes	
Chronic kidney disease	Patient with chronic kidney disease marked in electronic medical record	Qualitative	0: No 1: Yes	
Hepatitis B co-infection	Patient with repeated confirmed ICD-10 diagnosis of B181 Chronic type B viral hepatitis, no delta agent from the date of HIV diagnosis to the end of follow-up.	Qualitative	0: No 1: Yes	
Hepatitis C co-infection	Patient with repeated confirmed ICD-10 diagnosis of B182 Chronic viral hepatitis type C from the date of HIV diagnosis to the end of follow-up.	Qualitative	0: No 1: Yes	
Major depressive disorder	Patient with confirmed ICD-10 repeat diagnoses: F320, F321, F322, F323, F328, F329, F330, F331, F332, F333, F334, F338, F339, F340, F341, F348, F349, F380, F381, F388 or F39X from the date of HIV diagnosis to the end of follow-up		0: No 1: Yes	
Start date TAF/FTC/BIC	Medication start date TAF/FTC/BIC	Quantitative, continuous	dd/mm/yyyy	
End date TAF/FTC/BIC	Medication end date TAF/FTC/BIC	Quantitative, continuous	dd/mm/yyyy	
NAIVE for TAF/FTC/BIC	Patient whose first HIV treatment is TAF/FTC/BIC	Qualitative	0: No 1: Yes	
ARVT scheme prior to TAF/FTC/BIC	Name of ARVT scheme immediately preceding TAF/FTC/BIC used for HIV treatment	Qualitative	Text	
HIV viral load at baseline	The patient has HIV viral load results at baseline (+ or - 4 weeks) of TAF/FTC/BIC therapy.	Qualitative	0: No 1: Yes	
BHIV viral load at baseline value	HIV viral load value at baseline (+ or - 4 weeks) of TAF/FTC/BIC therapy	Quantitative, continuous	1, 1.5, 1.8, 2, n	
HIV viral load at week 24	The patient has HIV viral load results at week 24 (+ or - 2 weeks) of TAF/FTC/BIC therapy.	Qualitative	0: No 1: Yes	
HIV viral load value at week 24	HIV viral load value at week 24 (+ or - 2 weeks) of TAF/FTC/BIC therapy	Quantitative, continuous	1, 1.5, 1.8, 2, n	
HIV viral load at week 48	The patient has HIV viral load results at week 48 (+ or - 2 weeks) of TAF/FTC/BIC therapy.	Qualitative	0: No 1: Yes	
HIV viral load value at week 48	HIV viral load value at week 48 (+ or - 2 weeks) of TAF/FTC/BIC therapy	Quantitative, continuous	1, 1.5, 1.8, 2, n	
CD4 Lymphocyte count at baseline	The patient has CD4 Lymphocyte count results at baseline (+ or - 4 weeks) of TAF/FTC/BIC therapy.	Qualitative	0: No 1: Yes	
CD4 Lymphocyte count at baseline value	CD4 Lymphocyte count value at baseline (+ or - 4 weeks) of therapy with TAF/FTC/BIC	Cuantitativa, continua	1, 1.5, 1.8, 2, n	

CD4 Lymphocyte count at week 24	The patient has CD4 Lymphocyte count results at week 24 (+ or - 2 weeks) of TAF/FTC/BIC therapy.	Qualitative	0: No 1: Yes	
CD4 Lymphocyte count value at week 24	CD4 Lymphocyte count value at week 24 (+ or - 2 weeks) of therapy with TAF/FTC/BIC	value at week 24 (+ Quantitative, with TAF/FTC/BIC continuous		
CD4 Lymphocyte count at week 48	The patient has CD4 Lymphocyte count results at week 48 (+ or - 2 weeks) of TAF/FTC/BIC therapy.	0: No 1: Yes		
CD4 Lymphocyte count value at week 48	CD4 Lymphocyte count value at week 48 (+ or - 2 weeks) of therapy with TAF/FTC/BIC	Quantitative, continuous	1, 1.5, 1.8, 2, n	
HDL at baseline	The patient has high-density lipoprotein results at baseline (+ or - 4 weeks) of TAF/FTC/BIC therapy	Qualitative	0: No 1: Yes	
HDL value at baseline	High-density lipoprotein value at baseline (+ or - 4 weeks) of TAF/FTC/BIC therapy	Quantitative, continuous	1, 1.5, 1.8, 2, n	
HDL at week 24	The patient has high-density lipoprotein		0: No 1: Yes	
HDL value at week 24	High-density lipoprotein value at week 24 (+ or - 2 weeks) of TAF/FTC/BIC therapy	Quantitative, continuous	1, 1.5, 1.8, 2, n	
HDL at week 48	The patient has high-density lipoprotein results at week 48 (+ or - 2 weeks) of TAF/FTC/BIC therapy.	0: No 1: Yes		
HDL value at week 48	High-density lipoprotein value at week 48 (+ or - 2 weeks) of TAF/FTC/BIC therapy	Quantitative, continuous	1, 1.5, 1.8, 2, n	
LDL at baseline	The patient has low-density lipoprotein results at baseline (+ or - 4 weeks) of TAF/FTC/BIC therapy.		0: No 1: Yes	
LDL value at baseline	Low-density lipoprotein value at baseline (+ or - 4 weeks) of TAF/FTC/BIC therapy	Quantitative, continuous	1, 1.5, 1.8, 2, n	
LDL at week 24	The patient has low-density lipoprotein HDL results at week 24 (+ or - 2 weeks) of TAF/FTC/BIC therapy.	Qualitative	0: No 1: Yes	
LDL value at week 24	Low-density lipoprotein HDL value at week 24 (+ or - 2 weeks) of TAF/FTC/BIC therapy	Quantitative, continuous	1, 1.5, 1.8, 2, n	
LDL at week 48	at week 48 The patient has low-density lipoprotein results at week 48 (+ or - 2 weeks) of TAF/FTC/BIC therapy.		0: No 1: Yes	
LDL value at week 48	Low-density lipoprotein value at week 48 (+ or - 2 weeks) of TAF/FTC/BIC therapy	Quantitative, continuous	1, 1.5, 1.8, 2, n	
AST at baseline	The patient has aspartate aminotransferase results at baseline (+ or - 4 weeks) of TAF/FTC/BIC therapy.	Qualitative	0: No 1: Yes	
AST at baseline value	Aspartate aminotransferase value at baseline (+ or - 4 weeks) of TAF/FTC/BIC therapy	Quantitative, continuous	1, 1.5, 1.8, 2, n	
AST at week 24	The patient has aspartate aminotransferase results at week 24 (+ or - 2 weeks) of TAF/FTC/BIC therapy.		0: No 1: Yes	
AST value at week 24	Aspartate aminotransferase value at week 24 (+ or - 2 weeks) of TAF/FTC/BIC therapy	Quantitative, continuous	1, 1.5, 1.8, 2, n	

AST at week 48	The patient has aspartate aminotransferase results at week 48 (+ or - 2 weeks) of TAF/FTC/BIC therapy.	Qualitative	0: No 1: Yes	
AST value at week 48	Aspartate aminotransferase value at week 48 (+ or - 2 weeks) of TAF/FTC/BIC therapy	1, 1.5, 1.8, 2, n		
ALT at baseline	The patient has alanine aminotransferase results at baseline (+ or - 4 weeks) of TAF/FTC/BIC therapy.	Qualitative	0: No 1: Yes	
ALT value at baseline	Alanine aminotransferase value at baseline (+ or - 4 weeks) of TAF/FTC/BIC therapy	Quantitative, continuous	1, 1.5, 1.8, 2, n	
ALT week at 24	The patient has alanine aminotransferase results at week 24 (+ or - 2 weeks) of TAF/FTC/BIC therapy.	Qualitative	0: No 1: Yes	
ALT value week at 24	Alanine aminotransferase level at week 24 (+ or – 2 weeks) of TAF/FTC/BIC therapy	Quantitative, continuous	1, 1.5, 1.8, 2, n	
ALT week at 48	The patient has alanine aminotransferase		0: No 1: Yes	
ALT value at week 48	Alanine aminotransferase value at week 48 (+ or - 2 weeks) of therapy with TAF/FTC/BIC.	1, 1.5, 1.8, 2, n		
Total bilirubin at baseline	aseline The patient has total bilirubin results at baseline (+ or - 4 weeks) of therapy with Qualitative TAF/FTC/BIC.			
Total bilirubin value at	ubin value at Total bilirubin value at baseline (+ or - 4		1, 1.5, 1.8, 2, n	
baseline	weeks) of therapy with TAF/FTC/BIC.	continuous	, -, -, ,	
Total bilirubin at week 24	The patient has total bilirubin results at week 24 (+ or - 2 weeks) of therapy with TAF/FTC/BIC.	Qualitative	0: No 1: Yes	
Total bilirubin value at at week 24	Total bilirubin value at week 24 (+ or - 2 weeks) of therapy with TAF/FTC/BIC.	Quantitative, continuous	1, 1.5, 1.8, 2, n	
Total bilirubin at week 48	The patient has total bilirubin results at week 48 (+ or – 2 weeks) of TAF/FTC/BIC therapy	Qualitative	0: No 1: Yes	
Total bilirubin value at week 48	Total bilirubin value at week 48 (+ or – 2 weeks) of TAF/FTC/BIC therapy	Quantitative, continuous	1, 1.5, 1.8, 2, n	
Serum creatinine at baseline	The patient has baseline serum creatinine results (+ or – 4 weeks) of TAF/FTC/BIC therapy	Qualitative	0: No 1: Yes	
Serum creatinine value at baseline	Baseline serum creatinine value (+ or – 4 weeks) of TAF/FTC/BIC therapy	Quantitative, continuous	1, 1.5, 1.8, 2, n	
Serum creatinine at week 24	The patient has serum creatinine results at week 24 (+ or – 2 weeks) of TAF/FTC/BIC therapy	Qualitative	0: No 1: Yes	
Serum creatinine value at week 24	Serum creatinine value at week 24 (+ or – 2 weeks) of TAF/FTC/BIC therapy	TAF/FTC/BIC therapy continuous		
Serum creatinine at week 48	The patient has serum creatinine results at week 48 (+ or – 2 weeks) of TAF/FTC/BIC therapy Serum creatinine value at week 48 (+ or – 2	Qualitative	0: No 1: Yes	
Serum creatinine value at week 48	Quantitative, continuous	1, 1.5, 1.8, 2, n		

Glomerular filtration rate at baseline	The patient has the estimated glomerular filtration rate (eGFR) by CKD-EPI at baseline (+ or - 4 weeks) of TAF/FTC/BIC therapy	Qualitative	0: No 1: Yes
Value of glomerular filtration rate at baseline	Value of estimated glomerular filtration rate (eGFR) calculated by CKD-EPI at baseline (+ or - 4 weeks) of TAF/FTC/BIC therapy	Quantitative, continuous	1, 1.5, 1.8, 2, n
Glomerular filtration rate at week 24	The patient has an estimated glomerular filtration rate (eGFR) calculated by CKD-EPI at week 24 (+ or - 2 weeks) of TAF/FTC/BIC therapy	Qualitative	0: No 1: Yes
Glomerular filtration rate value at week 24	Value of estimated glomerular filtration rate (eGFR) calculated by CKD-EPI at week 24 (+ or - 2 weeks) of TAF/FTC/BIC therapy	Quantitative, continuous	1, 1.5, 1.8, 2, n
Glomerular filtration rate at week 48	The patient has the estimated glomerular filtration rate (eGFR) calculated by CKD-EPI at week 48 (+ or - 2 weeks) of TAF/FTC/BIC therapy	Qualitative	0: No 1: Yes
Glomerular filtration rate value at week 48	Value of estimated glomerular filtration rate (eGFR) calculated by CKD-EPI at week 48 (+ or - 2 weeks) of TAF/FTC/BIC therapy	Quantitative, continuous	1, 1.5, 1.8, 2, n
Number of medication claims	Number of TAF/FTC/BIC medication claims during the 48-week follow-up	Quantitative, discrete	1, 2, 3, n
Headache emergency	nergency The patient visited the emergency department during the period of TAF/FTC/BIC use for ICD-10 codes G444 and/or G448		0: No 1: Yes
Diarrhea emergency	The patient visited the emergency department during the period of TAF/FTC/BIC use for ICD-10 code A09X: Diarrhea and gastroenteritis of presumed infectious origin	ing the period of or ICD-10 code A09X: Qualitative enteritis of presumed	
Nausea and vomiting emergency	The patient visited the emergency department during the period of TAF/FTC/BIC use for ICD-10 code R11X: Nausea and vomiting	Qualitative	0: No 1: Yes
Termination of health insurance coverage	The patient terminated their health insurance with EPS SURA.	Qualitative	0: No 1: Yes
Date of termination of insurance coverage	Date of termination of health insurance with EPS SURA	Quantitative, continuous	dd/mm/yyyy
Death	The patient passed away after the index date	Qualitative	0: No 1: Yes
Date of death	Date of death Date of patient's death		dd/mm/yyyy

Sample Size

No sampling will be conducted, as data from the entire population (census) that meets the eligibility criteria for this study will be used.

Statistical Analysis

The database created in Access will be transferred to RStudio and Jamovi for the corresponding descriptive analysis.

Characterization of the Sociodemographic and Clinical Profile

Absolute and relative frequencies will be calculated for categorical variables. For numerical variables, normality will be assessed using the Shapiro-Wilk test. Variables with a p-value greater than 0.05 will be considered to follow a normal distribution and will be represented by means and standard deviations. For variables that do not follow a normal distribution, medians and interquartile ranges will be used.

Proportion of Pretreatment Regimens

The proportion of patients who have received different combinations of ART prior to starting TAF/FTC/BIC will be calculated. Frequency tables will be used to display the proportion of each pretreatment regimen, supplemented by bar charts reflecting the frequencies of the most common treatments.

Virologic Suppression at 24 and 48 Weeks

Virologic suppression is defined as a viral load of <50 copies/mL at weeks 24 and 48 of treatment. The proportion of patients achieving this threshold will be calculated at both time points, and the results will be compared between weeks 24 and 48 using McNemar's test for related samples.

Effective Access to Treatment

Effective treatment is defined as the initiation of therapy within a reasonable time after prescription. The time between prescription and the initiation of treatment will be calculated (mean or median, depending on the normality test), and patients will be classified into two categories: those who initiate treatment effectively (within a short period, generally defined as initiation within 7-14 days of HIV diagnosis) and

those who experience delays.

Paraclinical Results: CD4 T-Lymphocytes, Renal Function, and Lipid Profile

To describe changes in clinical markers at weeks 24 and 48, the summary measure (mean or median, depending on the normality test) of baseline values will be compared with the values of these biomarkers at the two time points. Paired-samples t-tests or Wilcoxon tests will be used if the data distribution is non-normal.

Rapid Onset of Therapy

The frequency of patients meeting this criterion will be calculated, and the characteristics of those with rapid onset versus those without will be compared using the chi-square test.

Treatment-Related Adverse Events

Treatment-related adverse events at weeks 24 and 48 will be characterized and classified according to type and severity. The proportion of patients experiencing these events will be calculated and compared between the two time points. Contingency tables and chi-square tests will be used to analyze the relationship between adverse events and other clinical and sociodemographic variables.

Adherence to Treatment

Adherence will be measured using pharmacy claims information with the Proportion of Days Covered (PDC). PDC calculates the proportion of days the patient has access to the medication over a specified period (64,65). In this study, patients with a PDC of 80% or higher will be considered to have adequate adherence. However, studies have shown that even lower adherence levels can still result in a high rate of viral suppression.

Biases

The following biases are considered potential risks in this study:

- Information Bias: This refers to errors introduced during the measurement of exposure, events, and other variables in the study population, which, if present, may lead to erroneous conclusions regarding the hypothesis being investigated. In this study, data obtained from secondary sources such as medical records may not fully or accurately capture the information of interest. To control for this bias, a random review of at least 10% of the clinical histories will be conducted, and the information recorded in the database will be cross-referenced with that found in the clinical records.
- Loss to Follow-up Bias: Loss of participants throughout the study may introduce bias, as the selection of participants is not random.

Statement on the Application of Ethical Principles in Research

In accordance with Resolution 8430 of 1993, this study is classified as risk-free: it involves retrospective documentary research techniques and methods, with no intervention or intentional modification of the biological, physiological, psychological, or social variables of individuals. The study will be conducted through the review of medical records and will be submitted for approval to the SURA Ethics Committee.

The use of medical records will be in compliance with Resolution 1995 of 1999, ensuring data protection and confidentiality of the information collected. Furthermore, a confidentiality agreement has been signed for academic projects, establishing compliance with legal provisions. This agreement confirms that access to personal data and confidential information from medical records will be provided, data which are considered sensitive under the "habeas data" law. The dissemination of this information could affect the privacy of the data owner. Therefore, all provisions outlined in this document will be strictly adhered to.

Timeline

Activity/Month	1	2	3	4	5	6
Phase 1: Research protocol writing						
Phase 2: Submission to IRB						
Phase 3: Execution (analysis and structuring of results and discussion)						
Phase 4: Technical report writing and closing to IRB						
Phase 5: Writing of publication-type manuscript and submission to journal and conference						

References

- 1. Challacombe SJ. Global inequalities in HIV infection. Oral Dis. 2020 Sep 1;26(S1):16–21.
- 2. del Rio C. The global HIV epidemic: What the pathologist needs to know. Vol. 34, Seminars in Diagnostic Pathology. W.B. Saunders; 2017. p. 314–7.

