As of January 2024, EPS SURA manages a cohort of approximately 15,300 HIV patients. The control, evaluation, and follow-up of these patients are primarily conducted by specialized healthcare institutions (IPS), with a smaller proportion monitored by affiliated IPS providers. Program indicators include treatment abandonment rates, virological success rates, virological success with ART in the last 3 months, HIV viral load, and CD4 T-lymphocyte levels in the past 6 months for patients with HIV. To assess patient adherence, regular weekly evaluations are conducted, which include laboratory monitoring and attendance at medical appointments. In cases of non-compliance, a strict follow-up plan is established by a designated physician and a pharmaceutical chemist to verify medication intake and evaluate risk factors associated with non-adherence on an individual basis. From 2020 to 2023, 169 patients within the HIV program were prescribed TAF/FTC/BIC treatment.

To date, few studies have been conducted in real-life conditions (19-22) to evaluate the effectiveness, safety, and clinical outcomes of TAF/FTC/BIC initiation, especially in patients at later stages of HIV, in everyday contexts. These outcomes are influenced by factors such as timely access to healthcare, follow-up, and proper adherence. No real-life studies have been conducted in Colombia, despite integrase inhibitors being the first-line treatment in the country and widely available as part of the mandatory health plan. Therefore, it is essential to evaluate the effectiveness, adherence, and clinical outcomes within our cohort. Generating our own data will allow us to create evidence with significant population impact.

Theoretical framework

Human Immunodeficiency Virus (HIV) is a retrovirus from the Retroviridae family,

specifically an enveloped positive-stranded RNA virus (5). There are two main types: HIV-1, the most common worldwide, and HIV-2, which is more prevalent in West Africa (23). The virus is transmitted through bodily fluids such as blood, semen, vaginal secretions, and breast milk. Once inside the body, HIV primarily targets CD4+ T lymphocytes of the immune system, binding to CD4 receptors and one of the chemokine co-receptors, CCR5 or CXCR4, to enter the host cell (6). This process of viral entry and replication leads to the progressive destruction of CD4+ T lymphocytes, resulting in severe immunodeficiency if not treated promptly (6,24).

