Bictegravir is a second-generation integrase strand transfer inhibitor (INSTI) used in HIV treatment. It is a key component of BikARVTy®, a fixed-dose regimen combining bictegravir, emtricitabine, and tenofovir alafenamide in a single daily tablet (52,53). This drug is notable for its high genetic barrier to resistance, meaning the virus is less likely to develop resistance to it compared to other INSTIs such as raltegravir and elvitegravir (54,55). It also has a limited drug-drug interaction profile, making it suitable for use in

combination with other antiretrovirals (52,56).

In phase 3 clinical trials, the bictegravir/emtricitabine/tenofovir alafenamide regimen has been shown to be non-inferior to dolutegravir-based regimens in both treatment-naïve and treatment-experienced patients, achieving effective virologic suppression without the emergence of resistance (53,57,58). Additionally, it is well tolerated and does not require prior HLA-B*5701 testing, which facilitates its rapid initiation in HIV treatment (53,57).

The most common adverse effects reported in clinical trials include diarrhea, nausea, and headache, with an incidence of at least 5% in treated subjects (59). Other less frequent adverse effects (\geq 2%) include fatigue, abnormal dreams, dizziness, insomnia, and abdominal distension (59). Regarding laboratory abnormalities, increases in serum creatinine, which stabilized throughout treatment, and increases in total bilirubin, mainly grade 1 and 2, were observed. Most adverse events were grade 1, and discontinuations due to adverse events were uncommon (59). Psychiatric events, such as suicidal ideation and depression, have also been reported, particularly in subjects with a history of psychiatric conditions. In subjects with end-stage renal disease, serious adverse events such as pneumonia and fluid overload were observed (59).

Objectives

General Objective: To estimate the clinical effectiveness and safety of HIV-positive patients on TAF/FTC/BIC treatment within an EPS in Colombia.

Specific Objectives:

- To characterize the sociodemographic and clinical profile of patients with HIV who initiate antiretroviral therapy with TAF/FTC/BIC.
- To identify the proportion of patients who have been on different pretreatment regimens before initiating TAF/FTC/BIC therapy.
- To assess the proportion of patients achieving virologic suppression at weeks 24

and 48 following the initiation of TAF/FTC/BIC therapy.

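### The 'Major depressive disorder' variable is defined by 21 ICD-10 codes, 8 of them outside F32 and F33, so its label is narrower than what it counts (minor)

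*Combined protocol and SAP*

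**What the plan says.** In the Variables table, the row labelled Major depressive disorder is coded 0 or 1. Its definition begins "Patient with confirmed ICD-10 repeat diagnoses: F320, F321, F322, F323, F328, F329, F330, F331, F332, F333" and continues "F334, F338, F339, F340, F341, F348, F349, F380, F381, F388 or F39X from the date of HIV diagnosis". The window closes at the end of follow-up. The table prints no titles for these codes and gives no reason for the breadth of the list. It has no separate row for other mood disorders.

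The variable feeds the first specific objective, the sociodemographic and clinical profile. For that objective the Statistical Analysis section says: "Absolute and relative frequencies will be calculated for categorical variables". Under Treatment-Related Adverse Events, the same section says that "chi-square tests will be used to analyze the relationship between adverse events and other clinical and sociodemographic variables". It does not list those variables.

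The cohort size is given under Problem Statement and Relevance: "From 2020 to 2023, 169 patients within the HIV program were prescribed TAF/FTC/BIC treatment".

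In the same table, Hepatitis B co-infection requires a repeated confirmed diagnosis with one code, described as "B181 Chronic type B viral hepatitis, no delta agent".

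**The concern.** A reader of the results will take a percentage headed major depressive disorder to refer to that diagnosis. The code list also admits patients whose only qualifying codes are in F34, F38 or F39. In ICD-10, the classification the plan uses, these are the persistent, other and unspecified mood-disorder categories. Such patients would be published under a diagnosis that their records do not carry.

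The planned quality control would not find this. The Data Collection Plan asks for agreement between codes and labels, and the Biases section provides for checking at least 10% of histories against the database. But an F39X that was correctly transcribed would pass a check against the record and still be counted under the wrong name. The fault is in the definition, so it has to be corrected there.

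At stake are one line of the clinical profile and any adverse-event cross-tabulation that uses this variable.

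**Working it through.** **Inputs.** The code list is from the Variables table. The maximum denominator, 169, is from Problem Statement and Relevance. The plan states no prevalence of depression, no sample-size basis and no share of patients by code, so there is no figure of its own to reproduce.

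**Step 1: count the codes by three-character category.**

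| Category | Codes listed | Number |
|---|---|---|
| F32 | F320, F321, F322, F323, F328, F329 | 6 |
| F33 | F330, F331, F332, F333, F334, F338, F339 | 7 |
| F34 | F340, F341, F348, F349 | 4 |
| F38 | F380, F381, F388 | 3 |
| F39 | F39X | 1 |

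The total is 6 + 7 + 4 + 3 + 1 = 21, with no duplicates. Inside F32/F33: 6 + 7 = 13. Outside: 4 + 3 + 1 = 8, and 8/21 = 38% of the codes.

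**Step 2: direction.** The 13 codes are a subset of the 21. Everyone who qualifies on the 13 also qualifies on the 21, so the 21-code count is at least the 13-code count. The two are equal if every flagged patient also qualifies on F32/F33 codes.

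**Step 3: effect of one patient.** With all 169 in the denominator, one patient flagged only through F34, F38 or F39 adds 1/169 = 0.59 percentage points. The exclusion criteria can only reduce the denominator, so 0.59 is the smallest contribution per patient.

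**Step 4: illustration under assumptions.** Suppose about 10% of 169 are flagged, that is 17 patients (17/169 = 10.1%), and let a share s of them carry only F34, F38 or F39 codes. Both figures are assumptions. Counts are rounded to whole patients.

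| s | Remaining on F32/F33 | Frequency | Difference (points) |
|---|---|---|---|
| 0% | 17 | 10.1% | 0 |
| 10% | 15 | 8.9% | 1.2 |
| 25% | 13 | 7.7% | 2.4 |
| 50% | 8 | 4.7% | 5.3 |

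Over the wider assumed range of 5% to 20% flagged and s from 0% to 50%, the difference runs from 0 to 10.1 points. The upper end is 34 flagged and 17 remaining: (34 − 17)/169 = 10.1 points. The width of this range shows that the documents do not fix the size.

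**Step 5: hepatitis B.** The label names hepatitis B co-infection without qualification, while the only accepted code excludes delta agent by its own description. A patient coded only as having hepatitis B with delta agent scores 0. The documents give no count from which to size this.

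**The case against.** The best defence is that nothing is hidden. The full list is printed, a broad code set is a legitimate way to find cases from records, and this is one descriptive comorbidity. The virologic suppression, adherence, CD4, renal and lipid analyses do not use it. All of this is right, and it is why the point is minor. It does not answer the mismatch, because a published table normally shows the label and not the code list.

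A second objection is that the plan does not print the category titles. That is correct; they come from ICD-10. But ICD-10 is the plan's own operational definition for this variable, and the division into five categories is visible in the codes themselves.

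A reader might draw four stronger conclusions, and the documents do not support them.

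- *The prevalence is overstated.* None is reported or assumed anywhere, and the excess over an F32/F33 definition may be zero. Against true prevalence even the direction is unknown, because the definition requires repeated diagnoses and the Biases section accepts that records may be incomplete.
- *38% of flagged patients are misclassified.* That figure is a share of codes and says nothing about how often each is used.
- *A planned adverse-event comparison by depression is compromised.* The wording is only to "analyze the relationship between adverse events and other clinical and sociodemographic variables"; depression is not named. The emergency-visit rows cover headache, diarrhoea, and nausea and vomiting, with none for psychiatric events.
- *The safety background requires mood disorders to be kept apart.* The HIV Treatment section says psychiatric events were reported "particularly in subjects with a history of psychiatric conditions", which treats psychiatric history as one broad group. If it bears on the list at all, it favours a wide one.

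**Conclusion.** The point holds as a mismatch between label and definition. Eight of the 21 codes fall outside F32 and F33, and a patient with only those codes, repeated, would be reported as having major depressive disorder. The frequency under that label can exceed what an F32/F33 definition would give and cannot fall below it. Each such patient contributes about 0.6 points with 169 in the denominator, slightly more after exclusions. The total cannot be sized from the documents, and the figures in the illustration rest on assumed inputs.

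If the variable is used in the adverse-event chi-square tests, which the generic wording allows but does not state, the comparison would carry the same mixed group.

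The conclusion assumes that major depressive disorder is meant to correspond to F32 and F33, and it takes the category meanings from ICD-10. The hepatitis B mismatch is real on the plan's own wording, but it is secondary and adds no weight to the main point. Overall severity is minor.

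**What to change.** Before extraction, do one of the following:

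- Limit Major depressive disorder to the listed F32 and F33 codes, and add a separate 0/1 variable, other mood disorder, for the F34, F38 and F39X codes.
- Keep the 21 codes, rename the variable depressive and other mood disorders, and use that name in every table.

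For hepatitis B, either add the code for chronic hepatitis B with delta agent or narrow the label to match the single code now listed.

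The cost is an edit to two rows of the Variables table and their code lists. Renaming needs no new data. Splitting needs one more column from records that are being searched anyway. The only downside is that the depression frequency may come out slightly lower under the first option.
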